Intrapartum maternal oxygen supplementation:

Effects on the mother and neonate

PI: [name] MD MS

Washington University in St Louis

Protocol- Version 14

June 11, 2021

Specific Aims

Intrapartum oxygen (O₂) supplementation is nearly ubiquitous on Labor and Delivery units, with over 60% of the 2 million laboring patients per year in the U.S. receiving supplemental O₂ at some point during labor(1). O₂ is most commonly administered to laboring patients with Category II electronic fetal monitoring (EFM) – a broad class of EFM used to identify patients at risk for fetal acidemia – with the theoretic rationale that maternal O₂ supplementation increases O₂ transfer to the fetus, thereby reversing hypoxia and preventing acidemia (2). This practice has become standard of care, yet there is no evidence of benefit and even concern for possible harm (1, 3-5). Therefore, there is an urgent need to fill this important knowledge gap.

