We propose a randomized controlled trial to investigate maternal and fetal free radical activity in laboring patients with Category II EFM exposed to O₂ or RA. A randomized controlled trial, the ‘gold-standard’ of study design, was chosen to produce high quality evidence on the safety of O₂ administration for Category II EFM. Our central hypothesis is that prolonged intrauterine exposure to O₂ during labor, compared with RA, generates free radicals that have downstream biochemical and clinical consequences to the neonate. This trial will be conducted on Labor and Delivery (L&D) at Washington University Medical Center (WUMC). Patients ≥37 weeks gestational age in active labor (≥6 centimeters cervical dilation) with Category II EFM necessitating intrauterine resuscitation (as determined by the care provider team) will be randomized to RA or maternal O₂ administration of 10L/min via nonrebreather face mask until delivery. All other resuscitation techniques (maternal repositioning, intravenous fluid bolus, etc) will be left to the discretion of the care provider team. EFM strips will be read and interpreted by the study nurse coordinator. Maternal blood, collected at randomization and within 1 hour post-delivery, placenta and umbilical artery blood collected at the time of delivery will be used to run MDA analyses. Maternal urine will be collection on enrollment (prior to rupture of membranes or cervical dilation <6cm), at time of randomization, and within 1 hour of delivery. At any of these time points, if patient has a foley catheter, the urine may be collected from the catheter. If patient does not have a catheter, either a straight catheterization can be performed or a clean catch sample can be obtained. The same commercially available assays used to quantify MDA and 4-HNE in our blood samples will be used for the urine samples.

Study staff will extract data from medical records including maternal demographics, antepartum history, intrapartum management, delivery outcomes, and neonatal outcomes. The patient’s primary nurse will perform real-time documentation of O₂ or RA initiation, any disruption in intervention, administration of amnioinfusion and additional resuscitation techniques performed (number of times patient is repositioned, total intravenous fluids, discontinuation of oxytocin).

Conduct of Trial

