Recruitment of Subjects and Randomization: We will use established recruitment techniques employed in recent RCTs performed on L&D at BJH. All women admitted to L&D in spontaneous labor or induction of labor will be screened with the above inclusion and exclusion criteria. Eligible subjects will be approached for written consent to participate on admission to L&D, irrespective of starting cervical dilation. Randomization will be performed only when the patient is in active labor (defined as cervical dilation ≥ 6 cm) and develops Category II EFM necessitating intrauterine resuscitation as determined by the care provider team (**Figure 3**). Using a computer-generated sequence in block sizes of 4, patients will be randomized in a 1:1 ratio to either O₂ or RA.

Figure 3: Enrollment and Randomization of Study Participants

Intervention

1. **O₂ group:** Patients in this group will receive O₂ via nonrebreather face mask at 10L/min (FiO₂ approximately 0.80) [55]
2. **RA group:** Patients in this group will be exposed to RA only and not wear an O₂ mask unless required for maternal hypoxia (FiO₂ approximately 0.21).

Primary Aim 1

Determine the effect of RA, compared with O₂, on maternal and fetal free radical activity.

1. **Hypothesis:** RA, compared with O₂, for Category II EFM in labor will result in lower mean maternal and umbilical cord levels of malondialdehyde, a byproduct of free-radical-mediated lipid peroxidation and a marker of oxidative stress.
2. **Rationale:** MDA and 4-HNE are downstream products of free radical buildup from excess O₂ and are known markers of oxidative stress.. The current use of O₂ for Category II EFM may result in prolonged exposure that generates free radicals and resultant oxidative stress.
To explore the feasibility of MDA analysis in laboring patients and to provide preliminary data for sample size calculation, we performed the Thiobarbituric Acid Reactive Substances (TBARS) assay for MDA quantification in a subset of maternal (n=27) and UA (n=33) samples exposed to O₂ in the above mentioned pilot trial. The mean maternal MDA was 6.5 μ M \pm 1.0 and the mean UA MDA was 8.3 μ M \pm 2.0. Although no conclusions regarding oxidative stress can be made from this data alone, these results demonstrate feasibility of MDA analysis in this setting.

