5. Data analysis: The primary analysis will be by intention-to-treat. Baseline demographics and secondary outcomes will be compared between RA and O₂ groups using χ^2 , Fisher exact test, Mann-Whitney *U* test, or Student's *t* test as appropriate. The primary outcome, mean maternal and UA MDA, will be compared between groups using the Student's *t* test if normally distributed. If non-normally distributed, the median maternal and UA MDA levels will be compared between groups using the Mann-Whitney *U* test. Linear regression will be used to adjust for relevant covariates. We will perform supplementary analyses including 1) stratified analysis by presence of maternal comorbidities or fetal growth restriction to assess if the effect of O₂ on oxidative stress varies in patients with fetal growth restriction or comorbidities. (2) as-treated analysis to determine whether compliance with the assigned group affects outcomes.
6. Sample size calculation: Based on pilot trial data, the mean UA MDA in 33 patients receiving O₂ for Category II EFM in active labor is $8.3 \pm 2.0 \mu\text{M}$. Assuming a two-sided alpha of 0.05, a total **212 patients (106 O₂ and 106 RA)** will afford 80% power to detect a 10% difference mean UA MDA between O₂ and RA groups, while accommodating for 15% loss due to UA samples. A 10% difference in UA MDA levels may be meaningful as neonatal MDA differences as small as 3-5% are associated with free-radical mediated injuries such as hypoxic ischemic encephalopathy [28, 57] There is limited published data on maternal MDA levels and associated adverse outcomes. However, this sample size will afford >90% power to also detect a 10% difference in maternal MDA between groups. To accommodate a compliance run-in of 6 patients, a total of **218 patients** will be recruited.

Feasibility of the sample size: BJH delivers approximately 4,000 patients per year. Based on results of our pilot trial, 32% of the approached patients meeting eligibility criteria consented to participation in the study. Of the patients enrolled, 40% met criteria for randomization (Category II EFM necessitating intrauterine resuscitation after 6cm dilation). In total, 114 patients were randomized over the study period of 12 months. Therefore, we anticipate successful enrollment of 212 patients within 2.5 years (70-72 patients/year).

Secondary Aim 1:

Investigate the relationship between duration of RA or O₂ exposure and magnitude of oxidative stress

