1C. Potential Risks: The proposed study involves potentially rare risks to the subjects, including loss of confidential health information, provision of poor feedback to families regarding outcome data, physical risks of serial blood draws, and excessive demands on patients. We anticipate minimal risk to the neonate by "withholding" oxygen treatment for Category II EFM because (1) the clinical evidence thus far suggests that oxygen provides no benefit, and (2) there were no adverse outcomes amongst neonates in the room air group of my pilot trial. Protections against anticipated risks are outlined below under "Adequacy of Protection Against Risk."

2. Adequacy of protection against risks-

2A. Recruitment and Informed Consent: Pre-screening for eligibility criteria via medical record review will be conducted, and potential participants will be approached on Labor and Delivery. None of the data obtained in pre-screening will be saved. The study design, expectations, and risks/benefits will be explained, and potential subjects will be given a written informed consent form by a study team member. Consent will be documented by using a signed consent form. Trained study team members will have sufficient time to explain the study and the informed consent carefully in a private room, and eligible patients may decide to enroll at any time as long as they still meet eligibility criteria. Of note, our team has significant experience recruiting patients and neonates as part of prior investigations in this population.

2B. Protections Against Risk- Oxygen administration for Category II EFM is the current standard of practice. The safety of randomization to room air for Category II EFM has been demonstrated by the preceding pilot trial. All neonatal adverse events will be reviewed by the data and safety monitoring board (DSMB), which will meet after 50% of participants have been recruited to review any adverse neonatal or maternal events among the study cohort and determine safety of continuing the study to completion. The PI will be responsible for reporting all adverse events to the IRB.

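### Oxygen given earlier in the same labor is neither excluded nor used in any analysis: the arm contrast may be diluted, and women may be banded on incomplete exposure in the duration aim

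*Combined protocol and SAP*

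**What the plan says.** Under Recruitment of Subjects and Randomization, consent comes early: "Eligible subjects will be approached for written consent to participate on admission to L&D, irrespective of starting cervical dilation". Allocation comes later: "Randomization will be performed only when the patient is in active labor (defined as cervical dilation ≥ 6 cm) and develops Category II EFM" that the care team judges to need resuscitation. For the period in between, section 2B (Protections Against Risk) describes usual care: "Oxygen administration for Category II EFM is the current standard of practice".

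The only O₂-related exclusion in Table 1 is maternal hypoxia. Nothing restricts O₂ before randomization or sets a washout.

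On data, the Overview has the primary nurse keep "real-time documentation of O₂ or RA initiation, any disruption in intervention". Study staff also extract intrapartum management from the record. Earlier O₂ is not named in either place.

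On analysis, Primary Aim 1 (item 5) compares the arms by intention-to-treat, adds a regression on covariates it does not list, and adds an as-treated analysis concerned with compliance with the assigned group. Maternal blood is drawn at randomization, but no analysis adjusts for that value. The duration aim (Secondary Aim 1 in Research Design and Methods, items 2 and 3) compares five bands of O₂ exposure, from under 30 to over 90 minutes, within the O₂ arm. It explains the spread of durations by when, after 6 cm, a woman is randomized. It does not say when the clock starts.

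**The concern.** A woman may receive O₂ at 5 cm, reach 6 cm, and then be randomized. By the protocol's own account of usual care this is foreseeable, and Secondary Aim 2 puts inductions at 70% of the cohort, so there is often time in hospital before active labor.

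Two analyses are exposed in different ways. In the arm comparison, such a woman allocated to RA is analyzed as room air although her markers may still reflect O₂. In the duration aim, such a woman allocated to O₂ may be placed by her minutes after randomization alone. The second matters more: that comparison lies within one arm, so randomization does not protect it, and section 4 (Importance of the Knowledge to be Gained) expects its result to guide future use of O₂ in labor.

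**Working it through.** **Inputs from the protocol (Primary Aim 1, items 2 and 6).** Two-sided alpha 0.05; 80% power; target difference 10%; UA MDA 8.3 µM, SD 2.0 (33 pilot women on O₂); maternal MDA 6.5 µM, SD 1.0 (27 pilot women on O₂); 15% loss of UA samples; 106 per arm.

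**Inputs not in the documents (assumed).** p = share of women with O₂ before randomization; c = share of the O₂–RA contrast lost in those women.

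**1. The plan's own figure.** UA difference δ = 0.10 × 8.3 = 0.83 µM. Per arm, n = 2(1.96 + 0.84)² × 2.0² / 0.83² ≈ 91.1; the t-based solution is 92.1. Then 92 × 1.15 = 105.8, or 106 per arm and 212 in total, as stated. For maternal MDA, δ = 0.10 × 6.5 = 0.65 µM, and 92 per arm gives 99% power, in line with the stated figure of more than 90%. Neither calculation allows for dilution.

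**2. Arm contrast.** Let earlier O₂ raise the delivery value by *a* in RA women and by *b* in O₂ women. The expected difference between arms is δ − p(a − b). If a = b, it is still δ. If earlier O₂ adds nothing in women who then receive O₂ anyway (b = 0, saturation) and a = cδ, it is δ(1 − pc). Two-sample t test, 92 per arm:

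| pc | UA difference (µM) | UA power | Maternal difference (µM) | Maternal power |
|---|---|---|---|---|
| 0 | 0.830 | 80% | 0.650 | 99% |
| 0.10 | 0.747 | 71% | 0.585 | 98% |
| 0.15 | 0.706 | 66% | 0.553 | 96% |
| 0.20 | 0.664 | 61% | 0.520 | 94% |
| 0.30 | 0.581 | 50% | 0.455 | 87% |

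For example, pc = 0.15 corresponds to p = 30% and c = 50%.

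**3. Duration bands.** Suppose a woman has 60 minutes of O₂ at 5 cm and 20 minutes after randomization. Her total is 80 minutes, which belongs in the 60–90 band. Counted from randomization she is in the under-30 band. The effect on the fitted relationship depends on its shape. Let D₁ and D₂ be minutes before and after randomization, and suppose the effect persists to delivery.

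- *Additive.* If the marker is A + β(D₁ + D₂), regressing it on D₂ alone gives slope β(1 + γ), where γ is the slope of D₁ on D₂. If the two are unrelated (γ = 0), the slope is unbiased and all bands shift equally. If women with more earlier O₂ have less afterward (γ < 0), the slope is flattened; if they have more (γ > 0), it is steepened. A simulation gave the same directions.
- *Saturating.* Suppose the effect levels off at 60 minutes. This is an assumption, although the protocol notes a pilot trend particularly over the first 60 minutes. A woman with 60 earlier minutes is then on the plateau in every band. If a share q of each band is like her, the rise over the first 60 minutes appears as (1 − q) of its true size; an assumed q of 0.30 gives 70%.

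**The case against.** The strongest reply is that earlier O₂ is a pre-randomization characteristic, balanced between arms on average, so intention-to-treat validly estimates the effect of allocation from randomization onward. That stands. A reader might infer that the arm comparison is biased; the documents do not support this. A smaller contrast would describe the women enrolled, and it arises only if a exceeds b in step 2.

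A reader might also infer that the bands do understate exposure. The protocol never fixes the start of the clock, and staff already extract intrapartum management, so earlier O₂ could be counted. Counting from randomization is only implied by the explanation of why durations vary. Nor is flattening automatic: under additive exposure unrelated to later duration, the slope is unchanged.

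The third tempting step is to take p from the Specific Aims, which speak of labor "with over 60% of the 2 million laboring patients per year in the U.S. receiving supplemental O₂ at some point during labor". That covers the whole of labor, including after 6 cm, and says nothing about use before randomization. The 10% difference is a chosen target rather than a known undiluted effect, and the pilot SD may already contain variation from earlier O₂. The power figures are therefore illustrations.

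Finally, the unlisted covariates could include prior O₂, and the maternal sample at randomization measures carry-over directly. But the plan commits to neither use, and UA blood and placenta have no baseline sample. The as-treated analysis does not help, because earlier O₂ is not a departure from the assigned arm.

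**Conclusion.** The point holds as a gap in the plan. Earlier O₂ in the same labor is foreseeable from the protocol's own description, is not excluded, and enters no analysis. The arm comparison is valid but may be diluted. UA MDA, which sets the sample size, has little margin (80% falling to 50% as pc goes from 0 to 0.30), while maternal MDA stays at 87% or more. These figures rest on assumed p and c and on saturation; with equal carry-over in both arms the contrast is not reduced.

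The duration aim carries the greater risk: it is not randomized and its clock is undefined. If time is counted from randomization, women with earlier O₂ are placed in too short a band. The relationship is then flattened if the effect saturates, and distorted in either direction if earlier and later O₂ are correlated (flattened if negatively, steepened if positively). The omission is certain; its size cannot be determined from the documents. It is worth correcting because the remedy is cheap.

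**What to change.** 1. **Data (Overview).** Add to the extraction of intrapartum management the start and stop times of any O₂ before randomization. A nurse log running from admission is not needed: with 40% of enrolled women randomized, it would cover about 212 / 0.40 = 530 labors.
2. **Duration aim (items 2 and 3).** Define the start of the clock. Build the bands on total O₂ minutes in labor, and in the regression enter minutes before and after randomization as separate terms.
3. **Arm comparisons (Primary Aim 1, item 5).** Name prior O₂ (yes/no and minutes) as a baseline covariate in the adjusted maternal and UA comparisons. Adjust maternal MDA and 4-HNE for the value at randomization, from blood already being drawn.
4. **Sensitivity.** Compare the randomized arms in women with no O₂ before randomization. Because prior O₂ is fixed before allocation, this subset and the adjustment in item 3 preserve the randomized comparison.

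The cost is one additional extracted item and a few sentences, with no extra patients or samples. The sensitivity comparison will have fewer women and less power. Whether earlier O₂ should bear on eligibility is for the investigators to decide.

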Anticipated challenges and safeguards: A potential limitation of the study is the inability to blind patients and healthcare providers to the allocation, however, the assessors will be blinded to allocation to limit bias in data analysis. Allocation concealment via use of opaque sealed envelopes will also limit selection bias. Bias could result from nurses and physicians managing subjects differently based on knowledge of their group assignment. To minimize this, providers will be specifically instructed to apply all other intrauterine resuscitation techniques as needed, irrespective of their group assignment. Any additional intrauterine resuscitation that is performed will be documented. To maximize adherence to protocol, we will conduct nursing and physician education sessions.

Protection of Human Subjects/Approvals

1. Risks to human subjects-

1A. Human subjects' involvement, characteristics, and design- The study will enroll 212 patients to investigate whether intrapartum O₂ administration in patients with Category II EFM is associated with oxidative stress. The study population will be English-speaking. Amongst the patients enrolled in the pilot trial, 77% were African American, 14% were Caucasian, 4% were Hispanic, and 5% were of other ethnicities. [name] and the other study members have completed the training module required by the WUSM Human Research Program Office and received education on the responsible conduct of research. The preceding pilot trial was approved by the IRB at WUSTL (IRB ID 201602164) and registered at ClinicalTrials.gov (ID NCT02741284).

1B. Sources of materials-

The study will involve collection of data from two key components:

- 1) Clinical Data Collection** from the medical records of mother and child. For all subjects, these data will be stored in a secure, password-protected REDCap database anonymized with study identifier only.
- 2) Maternal and cord blood samples**: All blood samples will be stored in a locked freezer that only the research team has access to. The maternal/ cord blood and placenta outcomes assessed in this study are additional materials collected for the purpose of the study and are not a part of routine prenatal care. Maternal and cord blood/placenta malondialdehyde levels are not used clinically and at present, cannot be directly linked to clinical outcomes. This will be disclosed to all study participants.

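### One printed block size of 4, in an open single-unit trial with a judgement-based trigger, lets someone who sees nearly every assignment deduce some later ones; varying and withholding the size is a cheap, minor improvement

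*Combined protocol and SAP*

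**What the plan says.** Recruitment of Subjects and Randomization gives the allocation rule: "Using a computer-generated sequence in block sizes of 4, patients will be randomized in a 1:1 ratio". No second size, stratification factor or restriction on who knows the size is mentioned. The same section says patients are "approached for written consent to participate on admission to L&D, irrespective of starting cervical dilation". Randomization follows later, in active labor, once Category II EFM is judged to be "necessitating intrauterine resuscitation as determined by the care provider team".

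The Overview places the trial on one Labor and Delivery unit. Anticipated challenges and safeguards concedes the "inability to blind patients and healthcare providers to the allocation" and relies on concealment: "Allocation concealment via use of opaque sealed envelopes will also limit selection bias". It adds that outcome assessors are blinded and that "providers will be specifically instructed to apply all other intrauterine resuscitation techniques as needed, irrespective of their group assignment".

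The sample size paragraph plans 212 patients, plus a further allowance: "To accommodate a compliance run-in of 6 patients". It does not say whether those 6 draw from the same sequence.

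**The concern.** Envelopes protect the next card. They do not protect against inference from cards already opened, and here an opened card shows at the bedside as a mask or no mask. With one known block size, the end of each block is determined by its beginning.

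Consent is already given when allocation becomes relevant, so choosing whom to consent by expected arm is not the issue. What remains discretionary is the trigger. In the pilot, 40% of enrolled patients reached it (Feasibility of the sample size). If the team called it earlier, later or not at all according to the arm they expected, the arms could differ in tracing severity and in time from randomization to delivery. Blinded assays and intention-to-treat analysis act after assignment and would not undo that. The instruction to providers covers other resuscitation measures after assignment, not the calling of the trigger. The maternal sample at randomization gives a baseline for maternal markers. Umbilical artery (UA) MDA, which sizes the trial, cannot have one.

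**Working it through.** **Inputs.** Block size 4 and 1:1 ratio (Recruitment of Subjects and Randomization). UA MDA 8.3 ± 2.0 µM, 10% difference, two-sided alpha 0.05, 80% power, 15% loss, 212 patients (Sample size calculation). Expected accrual 70-72 per year, or 212 in 2.5 years (Feasibility).

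**The plan's own figure.** The documents give no predictability figure; the sample size only sets the number of blocks. The difference is 0.10 × 8.3 = 0.83 µM. Per arm, 2 × (1.96 + 0.84)² × (2.0/0.83)² rounds up to 92; 92 × 1.15 = 105.8, so 106, and 212 in total. That matches the plan and gives 212/4 = 53 blocks.

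**Fixed blocks of 4, everything seen, size and boundaries known.** There are six equally likely orders.
- Certain: position 4 always; position 3 when the first two match (probability 1/3). Per block 1 + 1/3 = 4/3, so (4/3)/4 = 33.3%, and 53 × 4/3 = 70.7 of 212.
- Best guess by position: 50%, 66.7%, 66.7%, 100%; mean 70.8%.
- A running count of earlier assignments does as well, since completed blocks cancel.

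**Boundaries unknown, everything seen.** An observer who knows the size and treats the four possible starting points as equally likely is certain of 13.9% of the first 20 patients and 31.3% of all 212 (simulation). Blurred boundaries delay a full tracker but do not stop one.

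**Random blocks of 4, 6 and 8 (an assumed set, equal probability), everything seen, set of sizes known.** Repeated simulation gives 2.1% to 2.5% certain, about 5 of 212, and 68.0% best-guess accuracy.

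**Partial visibility.** If each earlier assignment is seen with probability q and the observer still knows every patient's position in the block, the certain share under fixed 4 is q²/3: 8.3% at q = 0.5 and 2.1% at q = 0.25. That knowledge of position is generous to the observer. For someone who simply keeps a running count of what was seen, simulation gives:

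| Share seen | Fixed 4 | Random 4/6/8 |
|---|---|---|
| 100% | 70.8% | 68% |
| 50% | 52.5% | 52.4% |
| 25% | 51.4% | 51.4% |

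**What a full tracker would need to do.** As an illustration, take a shift of half the design difference, 0.5 × 0.83 = 0.415 µM; the choice of half is an assumption. Acting only on certain calls, the UA MDA gap between patients called under expected O₂ and under expected RA would have to be 0.415/0.333 = 1.2 µM with fixed 4, and 0.415/0.0223 = 18.6 µM with 4/6/8. Acting on every best guess, it is 0.415/(2 × 0.708 − 1) = 1.0 µM against 0.415/(2 × 0.680 − 1) = 1.15 µM.

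**Cost in balance.** The largest arm difference goes from 2 to 4 if the switch is made at a block end, and up to 6 if made mid-block. At 108:104 the standard error ratio is √[(1/108 + 1/104)/(2/106)] = 1.0002; at 109:103 it is 1.0004.

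**The case against.** The best case against acting is that the change does little for any realistic observer. Best-guess accuracy moves only from 71% to 68% for a full tracker, and not at all for someone who sees half or fewer of the assignments. Tracking is also hard. A block spans about 2.5 to 3 weeks (52 × 4/84.8 to 52 × 4/70), many physicians manage the patients, and O₂ is in common use outside the trial, so a mask does not identify a trial patient. The documents do not say that bedside staff know the block size or see a list. If the 6 run-in patients share the sequence, boundaries are blurred as well. Covariate adjustment by linear regression is planned, though the covariates are not named. All of this stands, and it limits the gain to near-complete trackers.

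It does not remove the point. The documents neither prevent tracking nor keep the size from those who judge the trigger, and certain knowledge falls from about 71 to about 5 of 212 for an observer who does see everything.

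A reader might count as a safeguard the statement that "EFM strips will be read and interpreted by the study nurse coordinator". The documents do not support that: nothing says this reading precedes randomization or confirms the trigger, which stays with the care team.

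A reader might also infer that a third of allocations will in fact be known, or that the trial is biased. Neither follows. The third is a ceiling for one kind of observer, and no evidence of tracking or of altered triggering is given.

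**Conclusion.** The plan can be improved at low cost; it is not shown to be compromised. The 33.3% ceiling rests on a known size, known boundaries (or long observation) and sight of essentially every assignment. The benefit of varying the size is real for that observer and negligible for one who sees half or fewer. A material shift in UA MDA would need such a tracker acting consistently in one direction. The inference that varying the sizes would make allocation unpredictable also fails, since 68% best-guess accuracy remains for someone who sees everything. The weight is minor, and smaller still if few patients remain: the documents, at Version 14, do not say how many.

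**What to change.** For patients not yet randomized, starting at the end of a complete block:
- use randomly varying block sizes, for example 4, 6 and 8;
- hold the sizes in a restricted document rather than the protocol text;
- keep the sequence and the cumulative list of assignments from those who judge the trigger;
- state whether the 6 run-in patients use the same sequence.

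The cost is new envelopes, a documented switch point and one or two sentences. The maximum imbalance rises from 2 to 4, about 0.02% on the standard error. Sample size and analysis do not change. Running-count guessing from masks seen on the unit would remain possible.
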